Statement of problem: There is a strong crossway relationship between periodontitis and hypertension. Hypertension is the most prevalent of cardiovascular diseases and its prevalence is increased by the presence of periodontitis. Periodontal attachment loss is higher in hypertension patients when compared to healthy subjects. Both are examples of non-communicable diseases (NCDs), also known as chronic inflammatory diseases, they tend to be of long duration and are the result of a combination of genetic, physiological and environmental factors. The lack of an appropriate balance between these factors results in cellular changes as well as the levels of cytokines with subsequent changes in clinical manifestations of periodontal diseases. Both periodontitis and hypertension are associated with inflammation and an increase in specific proinflammatory cytokines.

Aim of the study: To investigate the correlation between the clinical parameters and the levels of Endocan and TNF- α in gingival crevicular fluid (GCF) before and after non-surgical periodontal therapy (NSPT) in stage II periodontitis patients with hypertension in comparison to non-hypertensive patients.

Materials and Methods

Clinical assessment of specific clinical parameters: plaque index, gingival index, probing depth, clinical attachment level (CAL) as primary outcome. Biochemical assessment of Endocan and TNF- α levels in GCF by Enzyme Linked Immunosorbent Assay (ELISA) as well as measurement of blood pressure at baseline and after 3 months as secondary outcomes.

II. Background:

Hypertension and periodontitis are part of a group of diseases called non-communicable diseases (NCDs), which are rising in prevalence due to an increasingly aging population. NCDs comprise 71% of global death.

Hypertension is defined as repeated office SBP values ≥ 140 mmHg and/or DBP ≥ 90 mmHg. It is a multifactorial disease, that can be caused by endothelial dysfunction (ED), oxidative stress, and inflammation. Periodontitis is a chronic multifactorial inflammatory condition affecting the tooth periodontium. In periodontitis, chronic inflammation occurs in reaction to untreated bacteria, and this is associated with continuous stimulation of the immune system which subsequently causes damage to the tooth supporting tissues. The damage is manifested clinically with gingival bleeding, foul odor, clinical attachment loss, tooth mobility and may lead eventually to tooth loss.

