“What is the effect of NSPT on the clinical periodontal parameters and its correlation to changes in GCF levels of Endocan and TNF- α in hypertensive periodontitis patients compared to non-hypertensive patients?”

PICOTS Elements:	
Patient/Problem	Stage II periodontitis patients with controlled hypertension.
Intervention	Non-Surgical periodontal therapy.
Comparator	Stage II periodontitis healthy individuals.
Outcome	-Clinical evaluation as a primary objective. -Biochemical evaluation as secondary objective. -Blood pressure measurement as secondary objective.
Time	-Baseline and 3 months (for clinical evaluation) -3 months (for biochemical analysis) -3 months (for blood pressure evaluation)
Setting	Faculty of Dentistry, Ain Shams University.

IV. Aim of the Study:

- 1- To correlate changes in GCF level of Endocan and TNF- α with changes in periodontal parameters after NSPT in both groups with clinical parameters.
- 2- The aim of the present study is to investigate changes in the levels of Endocan and TNF- α in stage II periodontitis patients with controlled hypertension in comparison to healthy subjects before and after NSPT.
- 3- To correlate blood pressure changes before and after NSPT.

Primary outcome:

Clinical evaluation of periodontal parameters plaque Index, gingival index, probing depth and clinical attachment level comparing between hypertensive and non-hypertensive groups.

Secondary outcome (s):

- Biochemical evaluation of GCF levels of Endocan and TNF- α in hypertensive and healthy subjects by ELISA.
- Systolic and Diastolic Blood pressure measurements before and after NSPT in hypertensive vs healthy individuals and check if NSPT reduces SBP and DBP.

Clinical Relevance:

To understand the role of NSPT in stabilizing the periodontal condition as well as reduce GCF levels of Endocan and TNF- α which will subsequently result in better hypertension control and improve the lifestyle.

V. Hypothesis:

Hypertension influences response to NSPT and GCF levels of Endocan and TNF- α .

VI. Ethical considerations

•Risk and discomfort of patients: This research will be conducted with considerations of patients' safety and with attempts to reduce patients' discomfort by reassurance.

•Minimization of the risk: Patients' baseline vitals will be taken before any clinical intervention to ensure patients' safety. Moreover, all medical operations will be conducted under standardized infection control

procedures.

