- **Criteria for Discontinuation of Study/patient:** Patients will be allowed to leave the study if he/ she didn't conform with the oral hygiene instructions, this will be ensured by 2 weeks, 4 weeks and 6 weeks follow-up after NSPT and assessing clinical parameters like Plaque index (PI) to determine how compliant is the patient with oral hygiene instructions. Patients with PI 2 will be eliminated. Patients with uncontrolled hypertension (SBP greater than or equal to 140mmHg and DBP greater than or equal to 90mmHg) will be eliminated.
- **Benefits to the Patients and to the Community:** Patients will receive NSPT and oral hygiene instructions with no cost. The community will benefit from this study by having a better diagnostic modality for moderate cases of periodontitis and preservation of dentition. NSPT is expected to improve patients' oral/overall health and quality of life and to be of relevance in the management of patients with hypertension.
- **Privacy:** All patients' identification including patient data and photographs will be locked and not shared.
- **Confidentiality:** Patient's data will be treated with utmost confidentiality. No personnel other than the researchers will have access to the patients' data.
- **Data Management:** All patients' data will be saved on researcher's personal laptop that are not connected to any internet connections and no copies will be made in any kind of database.
- **Consent Procedures if Applicable:** Any medical procedures and photographs will have a printed written consent form.
- **Patient Informed Consent Form:** A proper consent form will be formulated & signed by the patient before starting any procedure.

VII. Study Design:

Case-control study.

VIII. Materials and Methods:

- **Study Setting:** Faculty of Dentistry, Ain Shams University.
- **Sample Size Calculation:**

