A power analysis was designed to have adequate power to apply a two-sided statistical test of the null hypothesis that there is no difference would be found between tested groups regarding clinical evaluation. By adopting an alpha (α) level of (0.05), a beta (β) of (0.2) (i.e., power=80%) and an effect size (d) of (1.53) calculated based on the results of a previous study; the total required sample size (n) was found to be (26) cases. Total sample size was increased by (25%) to account for possible dropouts during follow-up intervals to be (34) cases (i.e., 17 cases per group). Sample size calculation was performed using G*Power version 3.1.9.7. Increase to 20 cases per group to compensate for dropouts. (28)

- **Eligibility criteria:**

Inclusion Criteria

1. Patients with stage II periodontitis and controlled hypertension (self-reported history of a diagnosis of HTN by a physician and blood pressure (SBP < 140 and DBP < 90).
2. Both genders aged from 30-70.
3. Minimum 20 natural teeth excluding third molars.
4. Good compliance with the plaque control instructions following initial therapy.
5. Availability for follow-up and maintenance program.

Exclusion criteria:

1. Smokers.
2. Pregnant and lactating females.

3. Patients with other systemic diseases, such as diabetes mellitus, rheumatoid arthritis and cancer.
(According to Cornell Medical Index-Health Questionnaire).
4. Patients taking antibiotic, anti-inflammatory, and immunosuppressive therapy during the preceding 3 months before the start of the trial and during the study.
5. Patients who have undergone any periodontal therapy in the last 6 months.

Justification for Exclusions:

To reduce any confounding factors and bias that may affect the results of this study.

Study procedures:

1- Details of the interventions, testing and follow up:

Group Case (I):

This group will include 20 patients diagnosed with stage II periodontitis and controlled hypertension. They will receive NSPT and oral hygiene measures will be instructed following treatment.

Group Control (II):

This group will include 20 patients diagnosed with stage II periodontitis and no hypertension. They will receive NSPT and oral hygiene measures will be instructed following treatment.

Study protocol and surgical steps:

1. Before enrollment, a detailed case history will be recorded.

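### The blood pressure rule for eliminating uncontrolled hypertension contradicts the protocol's own definitions; the control criteria need labelling, and age and sex are left unbalanced at recruitment

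*Protocol*

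**What the plan says.** **Blood pressure limits.** Three places in the protocol use 140 and 90 mmHg.

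- Section II (Background): "Hypertension is defined as repeated office SBP values ≥ 140 mmHg and/or DBP ≥ 90 mmHg".
- Section VIII, Inclusion Criteria, item 1, gives the limit for a controlled case: "self-reported history of a diagnosis of HTN by a physician and blood pressure (SBP < 140 and DBP < 90".
- Section VI, Criteria for Discontinuation: "Patients with uncontrolled hypertension (SBP greater than or equal to 140mmHg and DBP greater than or equal to 90mmHg) will be eliminated".

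Blood pressure is scheduled before treatment and at 3 months (section VIII, steps 2 and 9, and Outcomes Assessment). The visits at 2, 4 and 6 weeks assess plaque index and bleeding on probing.

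**Who is a control.** Section VIII has one inclusion list for the whole study. It opens with "Patients with stage II periodontitis and controlled hypertension". The description of Group II then reads: "This group will include 20 patients diagnosed with stage II periodontitis and no hypertension". The PICOTS table names the comparator as "Stage II periodontitis healthy individuals". No criterion states how absence of hypertension is established. Related information is collected: before enrolment "a detailed case history will be recorded", other systemic diseases are screened "According to Cornell Medical Index-Health Questionnaire", and blood pressure is measured in step 2.

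**Balance.** The groups are formed by hypertension status (section VII, case-control). Both sexes aged 30 to 70 may enter. The stated means of limiting confounding is the exclusion list: smokers, pregnant or lactating women, other systemic diseases, recent medication and recent periodontal therapy. Matching or stratified recruitment is not mentioned.

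**The concern.** The words controlled and uncontrolled should between them cover every patient in the hypertensive group. They do not, because the entry limit and the elimination rule both join systolic and diastolic pressure with *and*. The opposite of both pressures being below their limits is that at least one is not. A patient with only one raised pressure at the 3-month reading would meet the Background definition of hypertension and fail the protocol's definition of control, and would still be kept. Two people applying the protocol in good faith could decide differently about the same patient, and so analyse different sets of patients.

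The control group carries the contrast that the hypothesis in section V is about. Controlled cases must themselves read below 140/90, so a normal reading cannot separate a control from a treated case; only history can. The text collects history but does not tie it to control status.

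Finally, section V attributes any difference in response to hypertension. If the hypertensive group is also older, or differs in sex, that difference competes as an explanation. Adjustment can be planned later, but matching can only be arranged before recruitment.

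**Working it through.** **1. Blood pressure wording.** Inputs are the three passages quoted above. Take one example from each combination of systolic and diastolic pressure:

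| Reading | Meets entry limit (section VIII) | Eliminated (section VI) | In the hypertensive range (section II) |
|---|---|---|---|
| 135/85 | yes | no | no |
| 150/85 | no | no | yes |
| 135/95 | no | no | yes |
| 150/95 | no | yes | yes |

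The second and third rows are the gap: 2 of 4 combinations are neither controlled nor eliminated. If the entry and elimination wordings were complements, the number would be 0 of 4. At baseline the gap does no harm for cases, because a case at 150/85 fails the entry limit. After entry it matters, and the scheduled reading is the one at 3 months.

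**2. Inclusion list.** Item 1 requires hypertension and Group II requires its absence. No one can satisfy both, so read literally none of the 20 planned controls meets the list. The group descriptions and the PICOTS table show that item 1 is meant for cases.

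**3. Age and sex.** The protocol gives no age gap between the groups and no correlation of age with response, so the bias cannot be computed. The following only illustrates how it would scale, for age.

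- Spurious standardised difference: d = (age gap in SD) × (correlation r of age with response).
- Chance of a significant result when hypertension has no effect: two-sided 5% t-test, noncentral t with 2n − 2 degrees of freedom and noncentrality d × √(n/2).
- n = 20 per group is the planned recruitment; n = 17 is the smaller figure in the sample size section.

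| Assumed gap × r | d | n = 20 | n = 17 |
|---|---|---|---|
| 0.5 × 0.2 | 0.10 | 6% | 6% |
| 1.0 × 0.3 | 0.30 | 15% | 14% |
| 1.5 × 0.4 | 0.60 | 46% | 40% |

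With r = 0.1 and gaps of 0.5 to 1.5 SD, d is 0.05 to 0.15 and the rate at 20 per group is 5% to 8%.

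What coarse matching would do, again under assumptions: ages normal with scale 10, truncated to 30–70, two bands (30–49 and 50–70), 20 per group.

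| Gap before matching | Gap left within bands | r | Rejection before | Rejection after |
|---|---|---|---|---|
| 0.44 SD | 0.14 SD | 0.2 | about 6% | 5% |
| 0.89 SD | 0.29 SD | 0.3 | 13% | 6% |
| about 1.45 SD | 0.49 SD | 0.4 | 43% | 9% |

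**4. Misclassified controls.** Take the protocol's d = 1.53 and assume that hypertensive controls respond like cases. The shift shrinks to d × (1 − m) for a misclassified fraction m, and the mixed control group also has extra variance, so the power was simulated. For m = 10%, 20% and 30% it is about 0.98, 0.93 and 0.84 at 20 per group, and 0.96, 0.88 and 0.77 at 17.

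**The case against.** **A discontinuation rule need not mirror an entry limit.** True, and a sponsor may deliberately keep patients whose control slips. But section VI presents its limits as the meaning of uncontrolled hypertension, while section VIII gives the meaning of controlled. The two conflict as definitions, whatever is done with the patient. The objection does confine the effect to the period after entry.

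**The control criteria are clear enough.** A reader might infer that the protocol excludes every control, or has no means of recognising one. The documents do not support this. The group descriptions in the same section settle the intent, the Background section defines hypertension, and history and blood pressure come before suitability is decided. What is missing is an explicit link.

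**The confounding is hypothetical.** This largely stands. A reader might infer from the 46% that the comparison is badly biased. That figure needs a gap of 1.5 SD and a correlation of 0.4 together, and neither comes from the documents. With a weak correlation there is almost nothing to correct. No sex effect has been quantified. The protocol also restricts stage, tooth count, smoking and systemic disease, and age adjustment may be in an analysis plan that is not shown, so its absence is not held against the protocol. What remains is that no listed restriction balances age or sex, and that matching is a recruitment rule which cannot be added afterwards.

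**Conclusion.** The blood pressure contradiction is wrong as written and is the main point. Two of four pressure combinations are hypertensive under section II and not controlled under section VIII, yet do not trigger elimination under section VI. This rests on the text alone. How many patients it would affect cannot be told from the documents.

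The undivided inclusion list is a minor drafting fault. Its practical risk, some hypertensive controls, mainly dilutes the group difference: at the planned effect, power stays at or above 0.84 with 20 per group, and at about 0.77 with 17 per group in the worst case considered.

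The lack of any balancing of age or sex is a real gap in a non-randomised comparison, but of unknown size. The 6% to 46% range (6% to 40% at 17 per group) depends entirely on the assumed d of 0.1 to 0.6. It supports a cheap safeguard and does not show that the results would be biased.

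**What to change.** 1. **Reconcile the blood pressure wording** in sections II, VI and VIII so that controlled and uncontrolled leave no combination unassigned, or state that the difference is intended. Which wording stands is for the sponsor to decide. Cost: a text edit.
2. **Label the inclusion criteria by group.** Tie absence of hypertension in controls to both the case history already taken (no diagnosis or treatment) and the blood pressure already measured, since readings alone cannot separate controls from controlled cases. Cost: a text edit, with no new measurement.
3. **Keep a recruitment tally** so that controls are frequency-matched to cases on two broad age bands, and on sex where feasible, as a complement to any age adjustment in an analysis plan. Two bands by sex make 4 cells, about 20/4 = 5 cases each. No extra visits are needed. The drawbacks are slower control recruitment in the older band at a single self-funded centre, and some age difference left within bands (0.14 to 0.49 SD in the assumed scenarios).

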2. A calibrated standard aneroid sphygmomanometer. The average of 3 blood pressure values (systolic blood pressure SBP and diastolic blood pressure DBP), will be taken at 1 minute interval, this will be used in data analyses.

(2020 International Society of Hypertension Global Hypertension Practice Guidelines)

3. For all patients who are suitable for the study the following clinical evaluation parameters will be measured:
 - a) Plaque index (PI) (Silness&Löe, 1964)
 - b) Gingival index (GI) (Löe&Silness, 1963)
 - c) Probing depth (PD) (Caton, 1980).
 - d) Bleeding on probing (BOP) (Ainamo, 1985)
 - e) Clinical attachment level (CAL) (Ramfjord, 1967).
 - f) Standardized periapical radiograph. (Pananou, 2017)

Note: Full mouth assessment will be done and then the deepest site will be evaluated for the GCF sample.

4. Baseline GCF samples will be taken the day after patients were clinically evaluated to prevent contamination with blood related to the probing of inflamed areas.
5. The sample areas will be insulated with cotton rolls to prevent saliva contamination and all supragingival plaque will be eliminated. The paper strips will be placed into the periodontal pocket and then permitted to remain for 30 seconds.
6. All patients will undergo full mouth NSPT, this will be done using ultrasonic and hand instruments.
7. The patients will receive oral hygiene instructions including tooth brushing using modified bass technique. All patients will be provided with toothbrush (soft), toothpaste (signal) and interdental cleaning with dental floss or interdental brush.
8. Two weeks follow-up to ensure that appropriate oral hygiene instructions are followed. The clinical parameter to be assessed will be PI and BOP, patients with PI 2 and BOP $> 10\%$ will be eliminated from the study.
9. Then clinical evaluation, collection of samples and measuring of SBP and DBP will be performed at 3 months after NSPT in both groups.

Outcomes Assessment:

- Clinical assessment.
- Biochemical assessment.
- Blood pressure measurement.

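### The only pre-treatment blood pressure session appears to decide case entry and also to serve as the analysis baseline, so before-after BP change is exposed to regression to the mean

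*Protocol*

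**What the plan says.** **Entry.** Inclusion criterion 1 (Protocol VIII, Eligibility criteria) requires of cases a "self-reported history of a diagnosis of HTN by a physician and blood pressure (SBP < 140 and DBP < 90". The control group is described in Study procedures: "This group will include 20 patients diagnosed with stage II periodontitis and no hypertension". No BP limit for controls is listed. The Background gives a definition that implies one: "Hypertension is defined as repeated office SBP values ≥ 140 mmHg and/or DBP ≥ 90 mmHg".

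**Measurement.** In Study protocol and surgical steps, step 1 is the pre-enrolment history. Step 2 is the BP average of three readings, which "will be taken at 1 minute interval, this will be used in data analyses". Step 3 then begins "For all patients who are suitable for the study the following clinical evaluation parameters will be measured". GCF sampling follows on the day after the clinical evaluation (step 4), and NSPT comes later (step 6). Outcomes Assessment lists BP once before NSPT and once at 3 months. No separate screening BP is described. Ethical considerations adds that "baseline vitals will be taken before any clinical intervention", without saying whether this is another reading.

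**Use.** The BP secondary outcome is "Systolic and Diastolic Blood pressure measurements before and after NSPT in hypertensive vs healthy individuals and check if NSPT reduces SBP and DBP".

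**Elimination.** Criteria for Discontinuation (Protocol VI) removes patients whose SBP is at or above 140 and whose DBP is at or above 90. It does not say at which visit.

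**The concern.** The case entry limit is set on a variable that is later an outcome. Three readings a minute apart average out reading noise, but they share whatever makes BP high or low on that day. Patients with a hypertension history who fall below the limit on one occasion are selected partly for a low day, and on a later occasion they read higher on average. If the selecting reading is also the baseline, that rebound is counted as change after NSPT.

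Two questions are affected. The within-group question, whether NSPT lowers BP, takes the whole drift, and the drift works against the effect sought. The comparison of hypertensive with healthy patients takes the difference in drift, which does not cancel if cases lie nearer the limit than controls. A real fall in cases could be hidden, or cases could seem to respond worse. More patients would not remove a bias of this kind.

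**Working it through.** The protocol gives no BP mean, SD or expected change, so there is no BP figure of its own to reproduce. It supplies the limits 140 and 90, the step order and 20 patients per group. Every other input below is an assumption.

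**1. Drift from the SBP limit alone, no true change.** Let usual SBP have mean μ and between-person SD σ_b, and let visit-to-visit variation have SD σ_w. Put σ = √(σ_b² + σ_w²) and z = (140 − μ)/σ. For patients kept because the first reading is below 140,

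expected (3-month minus first reading) = (σ_w²/σ) × φ(z)/Φ(z).

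| Assumed group | μ | σ_b | σ_w | σ | z | Drift, mmHg |
|---|---|---|---|---|---|---|
| Case, low | 130 | 12 | 6 | 13.42 | 0.745 | 2.683 × 0.3022/0.7720 = 1.1 |
| Case, central | 135 | 12 | 8 | 14.42 | 0.347 | 4.438 × 0.3757/0.6356 = 2.6 |
| Case, high | 140 | 12 | 10 | 15.62 | 0 | 6.402 × 0.3989/0.5 = 5.1 |
| Control, low | 118 | 10 | 6 | 11.66 | 1.886 | 3.087 × 0.0673/0.9704 = 0.2 |
| Control, central | 120 | 10 | 8 | 12.81 | 1.562 | 4.998 × 0.1178/0.9408 = 0.6 |
| Control, high | 122 | 10 | 10 | 14.14 | 1.273 | 7.071 × 0.1775/0.8985 = 1.4 |

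**2. Both limits.** A simulation (2 million subjects per scenario) added DBP with assumed usual means of 84 (cases) and 76 (controls), between-person SDs 8 and 7, visit SD 5, and SBP-DBP correlations of 0.6 (usual level) and 0.5 (visit). In the central scenario cases drift +2.74 and controls +0.73, so the spurious difference is 2.74 − 0.73 ≈ 2.0 mmHg. Widening σ_w to 5–12 widens the case range to about +0.8 to +7.1. A control group with no BP limit at all drifts 0. If usual BP is similar in the two groups and both are screened, the difference is near 0: with σ_w = 8 and μ = 125 in each, cases +1.33 and controls +1.30.

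**3. The elimination rule, if applied at 3 months (central scenario).**

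| Elimination at 3 months | Cases, step 2 reading as baseline | Controls, same | Cases, separate baseline |
|---|---|---|---|
| None | +2.74 | +0.73 | 0.0 |
| SBP *and* DBP over (as written) | +2.05 | +0.60 | −0.47 |
| SBP *or* DBP over | 0.0 | 0.0 | −1.88 |

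As written, the rule shrinks the drift and leaves a group difference of 2.05 − 0.60 ≈ 1.4. Under an *or* reading both measurements are cut at the same limits, so the drift cancels, but only by discarding about 23% of cases on their outcome. About 5% of central-scenario cases meet the written rule at 3 months with no true change (about 3 to 7% as the assumed DBP mean varies).

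**4. Carry-over to the next day.** If the visit errors of the step 2 reading and a next-day reading correlate at an assumed 0.5, half the drift remains: 0.5 × 2.74 ≈ 1.4 mmHg.

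**5. Precision.** With 20 per group, the 95% CI half-width for the difference in mean change is 2.024 × SD × √(2/20). An SD of change of 10 gives 6.4 mmHg, 11 gives 7.0 and 16 gives 10.2.

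**The case against.** The strongest objection is that the double use is inferred. No sentence says that the step 2 average decides eligibility, and the vitals promised under Ethical considerations could be a second pre-treatment reading. This stands as a limit on certainty. It does not remove the point, because only one pre-NSPT BP session is described and it precedes the patients already called suitable.

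A reader might infer that the protocol builds in a fixed upward bias. The documents do not support that, because the elimination rule names no visit and, applied at 3 months, it reduces or cancels the drift. A reader might also count every case with a 3-month SBP of 140 or more as meeting that rule. It requires DBP to be over its limit too, which far fewer patients meet. Nor would a separate baseline guarantee zero bias: elimination at 3 months would then produce a false fall, and next-day readings may share visit error.

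BP is secondary, the study is sized on clinical evaluation, and a 2 mmHg bias lies well inside the likely confidence interval. All of that is true and limits the weight of the point. An unseen SAP might adjust for baseline BP. Which reading is taken at which visit is still a protocol matter, and adjustment does not settle the comparison of non-randomised groups whose usual BP may differ, since each regresses towards its own mean.

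**Conclusion.** The point holds in conditional form. The protocol does not separate the BP that admits cases from the BP that serves as baseline, and its step order points to one reading doing both. If it does, and nobody is removed on BP at 3 months, case SBP rises spuriously by about 1 to 5 mmHg, 2.7 centrally. The group difference is distorted by about 2 mmHg centrally, and by close to nothing if the groups have similar usual BP. These sizes rest entirely on assumed means and SDs. The net direction stays open until the timing of the elimination rule is stated. The consequence is confined to a secondary outcome that 20 per group will estimate imprecisely, but the bias is avoidable by design at little cost.

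**What to change.** - In step 2, state that the three-reading average is used for eligibility only.
- In step 4, add a second three-reading average, taken the same way in both groups at the GCF visit before NSPT, and name it the analysis baseline.
- Define BP change as the 3-month average minus that baseline.
- Keep the 3-month BP of every treated patient in the BP analysis, so that the outcome does not select who is analysed.
- Reconcile Inclusion criterion 1, step 2 and Criteria for Discontinuation: which reading decides entry, which is baseline, and at which visit the BP elimination applies. The wording needs attention too. Entry requires both values to be below their limits, elimination requires both to be at or above them, and the Background definition uses and/or, so a patient with one value over fails entry but does not meet the elimination rule.

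The cost is a few sentences and about three minutes of cuff readings at a visit already scheduled. Because a next-day reading may share some visit error with the first, the correction may be partial.
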